Introduction and rationale During Total Knee Arthroplasty (TKA), the joint is subjected to considerable stress, which has been shown to be related to a recruitment and activation deficit of the quadriceps femoris muscle. The explanation for this correlation lies in a complex mechanism called Arthrogenic Muscle Inhibition (AMI). So far, AMI has been directly studied only in sub-acute and chronic phase after TKA because of the invasive procedures employed in order to evaluate it; However, clinical observation and some experimental studies also suggest the presence of this phenomenon in the initial postoperative days. The aim of the study is to investigate possible differences in quadriceps muscular activity, which could be associated with AMI and which may be investigated in the acute phase; data acquisition will be made on the first and third days after surgery.

Population and selection criteria 15 healthy subjects and 15 patients on hold for TKA will be recruited between July and September 2019. The inclusion criteria will be: age greater than 18 years old and a recent TKA or revision of TKA. Those patients with arthrogenic muscle inhibition before TKA with QAB<6 and the subjects with conditions (other than those which led to the TKA) that could interfere with quadriceps muscle activation or with motor performance will be excluded from the study.

Design and duration Prospective observational study. It will start in July 2019 and the recruitment period should last until September 2019.

Aims The primary aim of this study is the evaluation of possible differences in quadriceps muscular activation after TKA. Subjects will be asked to perform different tasks in isometric contraction, keeping the biomechanical context constant. Secondly, the correlation between the primary aim and the pain referred by the patient, registered using the NRS scale, will be investigated along with the patient's functional ability, assessed by means of the Timed Up and Go Test (TUG). There will be three assessment sessions: the day prior to the TKA procedure and at one and three days postoperatively.

Statistical methods and data analysis

At the end of data acquisition, the normality and homogeneity of the demographic variables will be assessed, as will the outcome measures at baseline. Differences in the outcome measures will be investigated with the t student test (or with the related non-parametric tests) and by means of the mixed models repeated measures ANOVA test. Linear regression will be applied so as to evaluate the correlation between outcomes.

Ethical considerations

The study population will comprise subjects who have undergone TKA; they will be assessed in isometric contractions of quadriceps femoris in the acute phase after surgery. It is assumed that this type of evaluation does not lead to adverse events, since in terms of demands made on muscle and joints, it is comparable with the physiotherapeutic treatment administered to all patients twice a day after TKA. The aim of this study is to understand how the quadriceps activates in acute phase after TKA in order to identify the best physiotherapeutic approach for the initial postoperative days. Data acquisitions will be made so as to allow the patients to participate in both physiotherapy sessions.

For the study, the materials supplied to the Movement Analysis Laboratory of the Humanitas Clinic will be used. Each assessment session will last about 20 minutes.

Timing of the study

Recruitment of subjects: July– September 2019

Data analysis: September - October 2019

Report presentation: November 2019

2 Background and introduction

Total Knee Arthroplasty is currently considered an effective treatment in reducing pain, improving functional abilities and quality of life in patients with advanced-stage knee osteoarthritis and in other diseases affecting the knee joint [1] [2]. However, considering that TKA is recognised as major surgery, the knee joint is subjected to considerable stress. This has been shown to be related to a recruitment and activation deficit of the quadriceps femoris muscle, both in sub-acute phase (starting from two weeks after surgery) and chronic phase (up to one year if compared with the contralateral limb) [3] [4] [5] [6]. This complex mechanism is termed arthrogenic muscle inhibition (AMI), properly defined as the long-lasting inability to fully activate the quadriceps muscle in the absence of nerve damage, following surgery and/or traumatic injury of the knee joint [7]. Although AMI has to date been described only in sub-acute and chronic phase after TKA because of the invasive procedures employed in order to evaluate it, some researchers have investigated this phenomenon by inducing in healthy subjects the same symptoms which are characteristic of the immediate postoperative period following knee surgery. These studies report a positive correlation; in particular they have shown how, inducing inflammation, pain and increasing intra-articular pressure, a recruitment deficit of the quadriceps muscle arises [8] [9] [10]. Clinical practice and published scientific research indicate the presence of AMI also in the acute phase after TKA.

3 Rationale

For ethical reasons, there are no studies currently published that directly investigate the presence and the size of AMI in the initial postoperative days following TKA. Clinical practice, and the study of AMI in sub-acute patients and in experimental clinical conditions, indicate an activation deficit of the quadriceps from the first day following surgery. This study aims to evaluate the role that AMI could play in the postoperative acute phase after TKA, examining possible differences in the activation patterns of the quadriceps muscle between patients and healthy subjects.

The results could be useful to better manage the treatment of patients affected by a recruitment deficit of quadriceps muscle, by reducing motor impairment and by improving the quality and precision of the physiotherapy in the acute phase after TKA.

4 Aims

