4.2 Endpoints

4.2.1 Primary endpoint

The primary aim is to observe possible activation alterations of the quadriceps femoris, more specifically of the vastus medialis, lateralis and rectus femoris muscles, by means of electromyographic signal acquisition. The subject will be asked to perform different tasks in isometric contractions, without changing the biomechanical context. The subjects will be asked to perform a homolateral knee extension, a homolateral hip flexion, a contralateral hip extension with

a contemporary homolateral hip flexion. The activation of the three muscles will be recorded through surface electromyography (sEMG) with four channels (FREEEMG 1000, BTS SpA). The electromyographic surface sensors will be positioned following the European SENIAM guidelines regarding vastus medialis, lateralis and rectus femoris of quadriceps femoris homolateral in terms of surgery access, in order to evaluate the activation intensity during the different tasks [11].

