5.2 Exclusion criteria

- QAB (quadriceps activation battery) < 6 the day before the operation [12].
- neurological or musculoskeletal diseases (different from the causes that which led the patient to the TKA), which may interfere with the quadriceps muscle activation or with motor performance of the subject.
- Uncooperative subjects.

6 Design

Prospective observational study. See *Attachment A*.

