6.1 General design

The patients scheduled for TKA will be recruited through the criteria mentioned above; moreover, healthy subjects will be recruited as control group. The patients will be assessed through a motor ability test (TUG), a referred pain scale, and a quadriceps isometric contractions session recorded with surface electromyography. The assessment sessions will be conducted the day before the operation and on the first and third postoperative day. The control group will be exposed once to the same assessments, with the EMG applied on the quadriceps muscle of the dominant limb.

The sEMG data will be acquired by asking the subjects to perform the following tasks: "homolateral knee extension", "homolateral hip flexion" and "contralateral hip extension with a contemporary homolateral hip flexion". Each task will be repeated twice and the execution order will be randomized. The subject will be placed in the supine position and three bands will be positioned respectively at the level of the malleolus and the inferior margin of the patella in order to immobilise the inferior limb and ensure an isometric contraction of the quadriceps, while keeping

the biomechanical context unchanged. For each subject belonging to the two study groups, the same setting will be used. During the data acquisitions, every subject will be encouraged to perform each contraction with the maximum strength. The performance of tasks will be video recorded in order to monitor the correct execution.

The NRS scale will be administered to the patients after each quadriceps evaluation session, while the TUG test will be conducted the day before the operation and on the third day after surgery.

In the first and third day after surgery, the session will take place after 3pm in order to allow the patients to participate in both of the physiotherapeutic treatments provided by the Humanitas Clinic Institute.

The TUG test consists in asking the patient to stand up from a chair, walk at spontaneous speed, turn back at a cone placed at a distance of 3 metres and sit back down on the chair. The patient will be timed starting from the operator mark and stopping when the patient has resumed the seated position on the chair. The test will be performed once in a session, with a mock test before.

The NRS scale consists of one 10cm segment, numbered from 0 to 10 on which the subject has to quantify their pain perception where 0 equals “no pain” and 10 equals “the worse pain ever perceived”.

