10.2 Subject identification – Data protection

All data related to data acquisition and analysis and all the information related to each individual subject shall be handled in the strictest confidence and to the fullest extent of the applicable law. Privacy shall thus be safeguarded, and no information shall be made public. Each subject will be identified with an ID (*Attachment B*). The name and surname of the subject will not be required. The data required will pertain to sex and age. Only those personnel actively involved in the study will have access to the database. Each subject will be informed about data protection by means of an appropriate form in this regard (*attachment D*) and will be asked to sign an informed consent form in order to participate in the study.

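### Day 1 EMG differences could be partly or wholly residual regional block, and the supplied plan records nothing that would separate this from AMI

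*Combined protocol and SAP*

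**What the plan says.** **Purpose and definition.** Section 2 describes AMI as "properly defined as the long-lasting inability to fully activate the quadriceps muscle in the absence of nerve damage". Section 3 states: "This study aims to evaluate the role that AMI could play in the postoperative acute phase after TKA", to be examined by comparing quadriceps activation between patients and healthy subjects. The synopsis is more cautious and speaks of "possible differences in quadriceps muscular activity, which could be associated with AMI". AMI is the only mechanism that the document offers for a post-operative deficit.

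**Measure and timing.** The primary endpoint (4.2.1) is "to observe possible activation alterations of the quadriceps femoris, more specifically of the vastus medialis, lateralis and rectus femoris muscles", using surface EMG. Section 6.1 has subjects encouraged to contract as strongly as they can, and describes no nerve stimulation. It also says: "The assessment sessions will be conducted the day before the operation and on the first and third postoperative day". Post-operative sessions are held after 3pm so that patients can attend both physiotherapy treatments. Controls are assessed once.

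**Safeguards.** Section 5.2 excludes a low QAB score on the day before the operation. It also excludes "neurological or musculoskeletal diseases" that may interfere with quadriceps activation, other than the causes that led to the TKA. No post-operative neurological check is described.

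**Data and analysis.** Section 7.2 plans a repeated-measures mixed-model ANOVA with no named covariate, and linear regression of EMG on NRS and TUG. The data form is Attachment B, which is not in the supplied text.

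**The concern.** Voluntary EMG amplitude shows how much the muscle is activated. It does not show why activation is low. Reflex inhibition, a pharmacological block and a nerve lesion would all appear as reduced activity.

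The planned comparisons do not separate these causes. Controls have no operation, and the pre-operative session precedes the exposure. Day 3 helps only in part: a deficit that fades by day 3 fits either a block wearing off or AMI recovering, and one that persists fits either AMI or a nerve lesion.

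The secondary analysis is exposed too. The Background cites experimental work in which induced pain produces a recruitment deficit, so AMI would suggest lower EMG with higher pain. A patient under block may show low EMG with low pain, which pulls the EMG-NRS slope the other way.

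The results are meant to inform early post-operative physiotherapy, so a wrong attribution would matter. Without a record of the exposure, the question cannot be settled from the study data.

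**Working it through.** The plan has no figure to reproduce: 15 per group was set without an effect size, SD or power calculation (7.1). The check is therefore a reading of the text plus two illustrations on assumed values.

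**Step 1. What could separate block from AMI on day 1?**

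| Possible safeguard | What the text gives |
|---|---|
| Exposure recorded | No mention of anaesthesia, block, analgesia or hours since surgery |
| Post-operative neurological check | None described; QAB is dated to the day before surgery, and the neurological exclusion is a selection criterion |
| Measure specific to mechanism | Surface EMG in voluntary effort only |
| Comparator with the same exposure | None: unoperated controls and a pre-operative session |
| Session timed from anaesthesia | No: the 3pm rule follows the physiotherapy timetable |
| Adjustment in the model | No covariate named |

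**Step 2. Share of an observed fall that is block.** Assumed: a true day 1 fall of 20%, a fall of 50% in a patient with residual block, and k of 15 patients affected.

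Mean fall = 20 + (k/15) × (50 − 20). Share due to block = (mean fall − 20) / mean fall.

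| k | Mean fall | Share due to block |
|---|---|---|
| 0 | 20% | 0% |
| 1 | 22% | 2/22 = 9% |
| 2 | 24% | 4/24 = 17% |
| 3 | 26% | 6/26 = 23% |
| 5 | 30% | 10/30 = 33% |

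**Step 3. Could block alone give a significant result?** Assumed: no AMI at all, affected patients lose 50% of EMG amplitude, between-subject CV 0.3 to 0.5, 15 per group, two-sided 0.05 (the plan does not state sidedness). A simple two-group comparison is used.

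Mean drop = (k/15) × 0.5; d = mean drop / CV; chance of significance ≈ Φ(d × √(15/2) − 1.96).

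| k | Mean drop | Chance, CV 0.5 | Chance, CV 0.3 |
|---|---|---|---|
| 3 | 10.0% | 0.08 | 0.15 |
| 5 | 16.7% | 0.15 | 0.33 |
| 8 | 26.7% | 0.31 | 0.68 |
| 15 | 50.0% | 0.78 | >0.99 |

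For example, with k = 8 and CV 0.3, d = 0.267/0.3 = 0.89 and 0.89 × 2.74 − 1.96 ≈ 0.47, so the chance is 0.68. The approximation holds the SD equal in both groups and ignores the extra spread within a mixed patient group.

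By comparison, one new nerve lesion with an assumed 80% loss moves the patient mean by 0.8/15 = 5.3%. It would matter mainly for that patient and for the regressions. An exposure shared by most patients is the larger risk.

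**The case against.** Several points against the concern are sound and limit it.

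- **Reporting.** A reader might infer that any day 1 deficit would be reported as AMI. The documents do not support that. The endpoint is activation alterations, the synopsis says only that differences could be associated with AMI, and 7.2 has no rule that classes a patient or session as AMI. What stands is a risk of misreading, because section 3 ties the patient-control difference to AMI and names no other cause.
- **Definition.** A reader might take the nerve-damage clause to rule out block. A reversible block is not nerve damage, so the clause bears directly only on a new lesion. The definition also calls the inability long-lasting, so a deficit gone by day 3 does not clearly meet it. The difficulty with block is one of confounding and does not need the clause.
- **Data collected.** The sentence "The data required will pertain to sex and age" might seem to show that nothing else is recorded. It stands in 10.2, next to the statement that names are not required, and concerns personal data. The variable list is Attachment B, which may already hold these items.
- **Use of a block.** No section says that one is used. Patients are expected to attend physiotherapy on day 1, and the synopsis calls its demands comparable to the test. That makes a dense block less likely but does not exclude a partial one.
- **Neurological exclusion.** It carries no date in 5.2 and could in principle cover a new palsy. Even so, no re-check is described.
- **Size.** Every magnitude is assumed. With few patients affected, block alone would seldom give a significant result (0.08 to 0.15 for 3 of 15).

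**Conclusion.** The concern holds as a limit on interpretation. On the supplied text, a day 1 activation difference cannot be distinguished from residual block, and it could be misread as AMI. The planned description of activation differences is not itself invalid.

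The size is unknown. It is near zero if no limb block is in use. On the assumed values it reaches about a third of the observed fall with 5 of 15 affected. If the exposure were shared by all patients, it could produce a significant difference with no AMI present. The effect on the EMG-NRS regression is argued by direction only and has not been quantified.

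This is an inexpensive improvement to a preliminary study. If Attachment B already records the exposure, only the analysis and wording changes remain.

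**What to change.** 1. **Attachment B and 6.1.** Unless already present, extract from existing charts for the 15 patients: anaesthesia technique; any regional block or catheter on the operated limb, with its end time; analgesics given before the session; time of end of surgery; and any new neurological deficit charted by the ward team.
2. **Section 7.2.** Keep the main analysis as planned. Add a sensitivity analysis that repeats the day 1 EMG comparison and the EMG-NRS regression without sessions in which a block was still running or had recently ended, or in which a new deficit is charted. Fix the window for a recently ended block before the analysis.
3. **Reporting.** Describe day 1 results as activation differences, and attribute them to AMI only if they persist in the sensitivity analysis. Report how many sessions were set aside, and judge persistence on the estimate and its confidence interval, because fewer sessions alone can remove significance. If nearly all sessions are set aside, state that the day 1 difference cannot be attributed.

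The cost is a little chart extraction and a few sentences in 6.1 and 7.2. The downside is fewer day 1 sessions in the sensitivity analysis and so less precision there. A block's end time is only a proxy for residual motor effect, and charted deficits depend on routine ward observation. No change to anaesthetic or analgesic care is proposed.

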4.1 General aims

The objective of the study is to evaluate possible differences in quadriceps muscular activation after TKA during the acute phase, with a comparison with healthy subjects. Moreover, it will be investigated whether any correlation exists between the outcomes obtained, the pain reported by the patient and his or her functional ability.

4.2 Endpoints

4.2.1 Primary endpoint

The primary aim is to observe possible activation alterations of the quadriceps femoris, more specifically of the vastus medialis, lateralis and rectus femoris muscles, by means of electromyographic signal acquisition. The subject will be asked to perform different tasks in isometric contractions, without changing the biomechanical context. The subjects will be asked to perform a homolateral knee extension, a homolateral hip flexion, a contralateral hip extension with

a contemporary homolateral hip flexion. The activation of the three muscles will be recorded through surface electromyography (sEMG) with four channels (FREEEMG 1000, BTS SpA). The electromyographic surface sensors will be positioned following the European SENIAM guidelines regarding vastus medialis, lateralis and rectus femoris of quadriceps femoris homolateral in terms of surgery access, in order to evaluate the activation intensity during the different tasks [11].

4.2.2 Secondary endpoint

The secondary aim is to understand whether there is a correlation between the acquired surface EMG data and the pain referred by the patient and the patient's functional ability. The secondary outcomes will be the pain referred by the patient and the patient's functional ability. The referred pain will be assessed through the Numeric Rating Scale (NRS) at the beginning of every session. The functional ability will be assessed with the Timed Up and Go Test (TUG) on the third day post-surgery and via a descriptive analysis on the patient's deambulation autonomy, considering the following characteristics: ambulatory aids, need for supervision or assistance, and maximum distance covered.

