7.1 Sample Size

The primary outcome of this study is the EMG signal detected during different isometric contractions of the quadriceps muscle. In the published scientific literature, there is insufficient data to define the minimal statistically significant difference for this outcome. Therefore, it is not possible to calculate the sample size. Some studies exist which compare the muscular activation in the inferior limb between healthy subjects and patients who have undergone PTG, with 10 subjects for each group [13]. In this study, 15 healthy subjects and 15 patients will be recruited; it is estimated that this sample will be enough to obtain a preliminary valuation of the differences between groups.

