7.2 Analysis

The statistical analysis will be carried out at the end of the data collection, using the SPSS 20.0 software. The categorical variables will be described via mean and standard deviation or median and interquartile range. The normality of the demographic variables and the outcome measures will be evaluated through the Kolmogorov-Smirnov test.

The t Student test (with normal variables) or the Mann-Whitney test (with non-normal variables) will be used to verify the pre-intervention homogeneity of the demographic variables. The mixed models ANOVA test for repeated measures will be used to analyse possible differences inter-groups and intra-groups. A post hoc analysis will be conducted in the eventuality of significant outcomes. Linear regression will be used to investigate the correlation between the EMG outcomes and the secondary outcomes (NRS and TUG).

The threshold value for the statistical significance will be fixed at 0.05.

8 Withdrawal from the study

Subjects who decide to leave the study for any reason will be immediately excluded from it. The subjects will be also informed about the possibility of withdrawal from the study at every session provided for by the protocol, including during the planned follow-up period, giving prior notification to any of the experimenters. Data acquired from those subjects who do not complete the study will be excluded from the analysis.

9 Forms and procedures for the data collection and management

The demographic and outcome data will be input into an anonymous form within an Excel sheet (*Attachment B*). This data will be collected by two experimenters in order to minimise any errors and will be saved in password-protected electronic format.

10 Ethical considerations

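### Pre-operative TUG is collected under section 6.1 but has no stated role in the EMG–TUG regression, so a day-3 association cannot be told apart from one already present before surgery

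*Combined protocol and SAP*

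**What the plan says.** Three sections of the combined protocol and SAP bear on this.

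- **Section 4.2.2 (Secondary endpoint)** sets the aim: "The secondary aim is to understand whether there is a correlation between the acquired surface EMG data and the pain referred by the patient", and likewise with functional ability. It then fixes the measurement: "The functional ability will be assessed with the Timed Up and Go Test (TUG) on the third day post-surgery", plus a descriptive account of walking autonomy. No pre-operative TUG is named.
- **Section 6.1 (General design)** sets three sessions for patients: "The assessment sessions will be conducted the day before the operation and on the first and third postoperative day". For the TUG it is more specific: "while the TUG test will be conducted the day before the operation and on the third day after surgery". Controls are assessed once.
- **Section 7.2 (Analysis)** gives the whole specification in one sentence: "Linear regression will be used to investigate the correlation between the EMG outcomes and the secondary outcomes (NRS and TUG"). It names no time point, dependent variable, covariate, change score or analysis population. On error control it adds: "The threshold value for the statistical significance will be fixed at 0.05".

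On size, section 7.1 says: "In this study, 15 healthy subjects and 15 patients will be recruited".

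**The concern.** Sections 4.2.2 and 6.1 disagree on when the TUG is measured as an outcome, and section 7.2 does not settle the matter. Taking the endpoint definition and the analysis sentence together, the natural result is day-3 TUG regressed on EMG with nothing else in the model.

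A patient who moved slowly and had low quadriceps EMG before surgery will tend to show both on day 3. A day-3 regression would then find an association even if nothing after the operation linked activation to function. The study's stated interest is the acute phase, and section 3 hopes the results will guide early physiotherapy. For that use it matters whether the association is new or was carried over. The measurement that helps to separate the two is already scheduled.

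The silence in section 7.2 also leaves several choices open until after the data are seen: which TUG value, raw or change, and whether the once-assessed controls enter.

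**Working it through.** **No figure to reproduce.** Section 7.1 says of its own design: "Therefore, it is not possible to calculate the sample size". The documents give no effect size, SD, power or correlation. What follows is illustration under stated assumptions.

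**Inputs from the documents.** 15 patients; significance level 0.05 (two-sided assumed, as sidedness is not stated); TUG the day before surgery and on day 3; EMG at both of those sessions.

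**Inputs assumed.** Pre-operative EMG–TUG correlation ρ = -0.5 or -0.7. Correlation k between the pre-operative and day-3 value of the same measure (tracking), 0.6 to 0.8 for both EMG and TUG. No post-operative link: given the pre-operative values, day-3 EMG and day-3 TUG are independent.

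**Step 1: induced day-3 correlation.** It equals k × k × ρ.

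**Step 2: compare with the critical value.** With n = 15, t(0.975, 13 df) = 2.160, so |r| must exceed 2.160/√(13 + 2.160²) = 0.51 to be significant.

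**Step 3: simulate both regressions at n = 15.** Repeated runs agree to about one percentage point.

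| ρ | k | Induced r | Unadjusted significant | Adjusted for pre-operative TUG |
|---|---|---|---|---|
| -0.5 | 0.6 | 0.36 × -0.5 = -0.18 | about 10% | about 5% |
| -0.5 | 0.8 | 0.64 × -0.5 = -0.32 | about 22% | about 5% |
| -0.7 | 0.6 | 0.36 × -0.7 = -0.25 | about 14% | about 5% |
| -0.7 | 0.8 | 0.64 × -0.7 = -0.45 | about 40% | about 5% |

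**Step 4: a second model.** Let pre-operative TUG alone drive both day-3 measures. The induced correlation is then the product of its correlations with day-3 TUG and day-3 EMG. For 0.3 × -0.3 = -0.09, 0.5 × -0.5 = -0.25 and 0.7 × -0.7 = -0.49, the unadjusted regression is significant in 6%, 14% and 48% of studies. The adjusted one is at about 5% throughout. At the low end there is little to correct.

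**Step 5: imperfect baseline.** The 5% is built into both models, because observed pre-operative TUG is assumed to carry all the confounding. If it measures underlying mobility with reliability 0.8, the adjusted rate is 7% to 11%. At reliability 0.6 it is 12% to 22%. (Assumed loadings: 0.7 to 0.8 for day-3 TUG, 0.5 to 0.7 for EMG.)

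**Step 6: cost of the covariate.** By Fisher's z, the correlation detectable with 80% power is tanh((1.96 + 0.84)/√12) = 0.67 without the covariate and tanh((1.96 + 0.84)/√11) = 0.69 with it. Collinearity costs more. If EMG and pre-operative TUG correlate at -0.5, the standard error of the EMG slope grows by 1/√(1 - 0.25) = 1.15; at -0.7, by 1/√(1 - 0.49) = 1.40.

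**Step 7: power.** Take a standardised EMG slope of 0.5 and baseline coefficients of 0.3, 0.5 and 0.7. If pre-operative TUG is uncorrelated with EMG, unadjusted power is 50% and adjusted power about 52%, 62% and 85%. With the same slope and residual variance but an EMG–baseline correlation of -0.5, adjusted power is 42%, 51% and 76%. At -0.7 it is 31%, 38% and 61%.

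**The case against.** The best case for the plan has four parts.

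*The baseline is not excluded.* A reader might infer that the plan rules out the pre-operative TUG. It does not: section 4.2.2 never says that day 3 is the sole time point, and section 7.2 is silent on covariates. This stands. The defect is that no role is specified.

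*The aim is a correlation.* A reader might infer that the regression is meant to estimate the effect of surgery on function and mixes it with earlier mobility. The documents never set that target. For a descriptive aim the unadjusted day-3 association is legitimate, and adjusting for baseline answers a different question. This also stands, and is why the unadjusted result should be kept. It does not help a reader who wants to know whether the link belongs to the acute phase.

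*The benefits cannot be added together.* A reader might infer that adjustment also raises power. The gain in step 7 requires pre-operative TUG to be uncorrelated with EMG, whereas the false associations in step 3 require the two to be correlated. No power gain should be claimed.

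*Adjustment is imperfect and every correlation is assumed.* Both parts are correct. Section 6.1 has the TUG timed once per session after a mock test, so measurement error is likely and some confounding would remain. Adjustment reduces the problem but may not remove it.

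**Conclusion.** The point holds as a gap in specification with a real consequence for interpretation. Sections 4.2.2 and 6.1 differ on the TUG time points, and section 7.2 gives the pre-operative value no role. The analysis as written therefore cannot distinguish a pre-existing EMG–function association from a post-operative one.

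The size depends wholly on assumed correlations. In the main illustration, with 15 patients, the chance of a significant result without any post-operative link is two to eight times the nominal 5% (10%/5% to 40%/5%). Under weak correlations it is close to nominal. The contrast with about 5% after adjustment holds only so far as pre-operative TUG captures the confounding.

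The endpoint is secondary and the study preliminary, so this should be corrected but does not touch the primary EMG comparison.

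**What to change.** 1. In section 4.2.2, reconcile the TUG time points with section 6.1: the day before surgery and day 3.
2. In section 7.2, state that, in patients only, day-3 TUG will be regressed on day-3 EMG with day-before TUG as a covariate, that the unadjusted association will be reported beside it, and that both are exploratory.

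The change takes about one sentence in each section and no new data. Its statistical price is one degree of freedom, and wider intervals for the EMG slope if EMG and pre-operative TUG are correlated. Neither a log transform of TUG nor a change-in-EMG model is needed: nothing in the documents argues for the first, and the second would add tests for which section 7.2 makes no multiplicity provision.
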